8.7.2. Primary Analysis: Study Objective 1-Awareness (Receipt) and Utilisation

Per question analysis: The number and proportion of HCPs self-reporting that they received and utilised each of the 4 aRMM materials (3 in Germany) will be reported. If appropriate, the number and proportion of HCPs self-reporting that they received and utilised the aRMM materials will be reported by ever and after February 2020 or January 2020 in Poland (except for the website, which will be reported by “ever” only). The number and proportion of HCPs self-reporting that they received information related to the Xeljanz Prescriber Website and that they utilised the website will also be reported.

Overall: The self-reported number of aRMM materials received per HCP and the self-reported number of aRMM materials utilised per HCP will be summarized continuously using means, SDs, medians, ranges, and interquartile ranges (IQRs).

8.7.3. Primary Analysis: Study Objective 2—Knowledge of Key Risk Messages

	RA/PsA Survey	UC Survey
Per question analysis	The number and proportion of HCPs providing a correct answer for each of the 18 knowledge questions will be reported.	The number and proportion of HCPs providing a correct answer for each of the 20 knowledge questions will be reported.
Overall	The number and proportion of HCPs providing correct answers to <13, 13-14, 15-16, 17, and 18 out of the 18 knowledge questions will be reported. The number of correct answers to the 18 knowledge questions per HCP	The number and proportion of HCPs providing correct answers to <14, 14-15, 16-17, 18-19, and 20 out of the 20 knowledge questions will be reported. The number of correct answers to the 20 knowledge questions per

090177e199ebc283\Approved\Approved On: 11-Apr-2022 22:32 (GMT)

	RA/PsA Survey	UC Survey
	will also be summarized continuously using mean, SD, median, range, and IQR.	HCP will also be summarized continuously using mean, SD, median, range, and IQR.

8.7.4. Primary Analysis: Study Objective 3-Adherence to the Risk Minimisation Practices Recommended in the aRMM Materials

	RA/PsA survey	UC survey
Per question analysis	The number and proportion of HCPs providing a desirable response for each of the 17 adherence questions will be reported.	The number and proportion of HCPs providing a desirable response for each of the 17 adherence questions will be reported.
Overall	The number and proportion of HCPs providing desirable responses to <12, 12-13, 14-15, 16, and 17 out of the 17 adherence questions will be reported. The number of desirable responses to the 17 adherence questions per HCP will also be summarized continuously using mean, SD, median, range, and IQR.	The number and proportion of HCPs providing desirable responses to <12, 12-13, 14-15, 16, and 17 out of the 17 adherence questions will be reported. The number of desirable responses to the 17 adherence questions per HCP will also be summarized continuously using mean, SD, median, range, and IQR.

8.7.5. Secondary Analysis: HCP Practice Characteristics

HCPs’ responses to the questions (2 pre-survey and 7 in the RA/PsA survey and 6 in the UC survey) related to HCP practice characteristics will be presented descriptively using frequencies and proportions.

8.7.6. Secondary Analysis: Attitude Towards the aRMM Materials

For each aRMM material and the Xeljanz Prescriber Website, among the HCPs who self-reported receiving the aRMM material or who were aware of the Xeljanz Prescriber Website, the number and proportion of HCPs finding the aRMM materials or Xeljanz Prescriber Website “Very Useful,” “Somewhat Useful,” or “Not Useful” will be described. These categories may be collapsed, as needed, after reviewing the distribution of the data.

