8.7. Data Analysis

8.7.1. General Statistical Consideration

Detailed methodology for summary and statistical analyses of data collected in this study will be documented in a statistical analysis plan (SAP), which will be dated, filed, and maintained by the Sponsor. The SAP may modify the analyses outlined in this protocol; any major modifications of primary endpoint definitions or their analyses will be reflected in a protocol amendment.

The data collected from the RA/PsA survey will be analysed separately from the data collected from the UC survey. For each survey (RA/PsA and UC), all primary analyses will be conducted using the *pooled* data from all countries, specialties (applies to the RA/PsA survey only), and indications (applies to the RA/PsA survey only), and will be descriptive in nature; no statistical comparisons within or between countries, specialties, and/or indications will be conducted. Only submitted and completed surveys—i.e., all of Questions of the survey (Appendix 1 and Appendix 2 [HCP Questionnaire for the RA/PsA survey and the UC survey, respectively]) answered (taking into account skip patterns) by HCPs eligible to participate in the survey—will be used in the analyses.

Categorical variables will be presented using frequencies and proportions. For most outcomes, associated 95% CIs will also be calculated; 95% CIs will *not* be calculated for outcomes such as attitude towards the aRMM materials and Xeljanz Prescribe Website and source of HCPs’ information on the safety of Xeljanz. Continuous variables will be presented using means, standard deviations (SDs), minimums, 25th percentiles, medians,

75th percentiles, and maximums. Depending on the sample size, stratification by country, number of patients treated with Xeljanz, experience prescribing Xeljanz (a proxy for indication), receipt and utilisation of the aRMM materials, and/or number of years in practice may be performed. The analysis may also be restricted to HCPs without prior experience as a healthcare professional in a Xeljanz clinical trial, if sample size is sufficient.

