a	Educational materials (documents designed for the patient and the physician, such as the tofacitinib prescriber brochure, the prescriber initiation and maintenance checklists, and the patient alert card)	
b	Summary of Product Characteristics (Label)	
c	National Health Authority website/National formulary website	
d	Pharmaceutical company website	
e	Do not know/recall the source	
f	Other	

Data: Single punch.

Data: Answer options will be displayed in a random order for each survey participant, with an exception for "Do not know" and "Other" – always keep these as the last two options.

[QUESTIONS ABOUT AWARENESS (RECEIPT) AND UTILISATION OF TOFACITINIB aRMM MATERIALS]

[QUESTION APPLIES TO ALL COUNTRIES]

Q13.1a. Have you ever received a **prescriber brochure for tofacitinib**? Please select one.

- Yes
- No
- I don't remember

Data: Single punch.

[QUESTION APPLIES TO ALL COUNTRIES, EXCEPT POLAND]

Q13.1b. The **prescriber brochure for tofacitinib** was updated in 2020. Did you receive a prescriber brochure after February 2020? Please select one.

- Yes
- No
- I don't remember

Data: Single punch.
Ask only if Yes in Q13.1a.

[QUESTION APPLIES TO POLAND ONLY]

Q13.1b. The **prescriber brochure for tofacitinib** was updated in 2020. Did you receive a prescriber brochure after January 2020? Please select one.

- Yes
- No
- I don't remember

Data: Single punch.
Ask only if Yes in Q13.1a.

[QUESTION APPLIES TO ALL COUNTRIES]

Q13.2. Have you read the **prescriber brochure for tofacitinib**? Please select one.

- Yes, all of it
- Yes, some of it
- No, I did not read it
- I don't remember

Data: Single punch.

Ask only if Yes in Q13.1a.

[QUESTION APPLIES TO ALL COUNTRIES]

Q13.3. How useful or not useful do you find the **prescriber brochure for tofacitinib** in your clinical practice?

- Very useful
- Somewhat useful
- Not useful

Data: Single punch.

Ask only if Yes in Q13.1a.

[QUESTION APPLIES TO ALL COUNTRIES EXCEPT GERMANY]

Q14.1a. Have you ever received the **prescriber treatment initiation checklist for tofacitinib**? Please select one.

- Yes
- No
- I don't remember

Data: Single punch.

[QUESTION APPLIES TO ALL COUNTRIES EXCEPT GERMANY and POLAND]

Q14.1b. Did you receive the **prescriber treatment initiation checklist for tofacitinib** after February 2020? Please select one.

- Yes
- No
- I don't remember

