- I don't remember

Data: Single punch.

[QUESTION APPLIES TO GERMANY ONLY]

Q14.1.i.b. Did you receive the **prescriber treatment checklist for tofacitinib** after February 2020? Please select one.

- Yes
- No
- I don't remember

Data: Single punch.
Ask only if Yes in Q14.1.i.a.

[QUESTION APPLIES TO GERMANY ONLY]

Q14.2.i. How often do you use the **prescriber treatment checklist for tofacitinib** when writing a **new prescription** of tofacitinib for a patient? Please select one.

- All of the time
- Most of the time
- Some of the time
- Never

Data: Single punch.
Ask only if Yes in Q14.1.i.a.

[QUESTION APPLIES TO GERMANY ONLY]

Q14.3.i. How often do you use the **prescriber treatment checklist for tofacitinib** when writing a **maintenance prescription** of tofacitinib for a patient? Please select one.

- All of the time
- Most of the time
- Some of the time
- Never

*Data: Single punch.
Ask only if Yes in Q14.1.i.a.*

[QUESTION APPLIES TO GERMANY ONLY]

Q14.4.i. How useful or not useful do you find the **prescriber treatment checklist for tofacitinib** in your clinical practice? Please select one.

- Very useful
- Somewhat useful
- Not useful

*Data: Single punch.
Ask only if Yes in Q14.1.i.a.*

[QUESTION APPLIES TO ALL COUNTRIES]

Q16.1a. Have you ever received a supply of **tofacitinib patient alert cards**? This is a card which is designed to be given to patients. Please select one.

- Yes
- No
- I don't remember

Data: Single punch.

[QUESTION APPLIES TO ALL COUNTRIES. EXCEPT FOR POLAND]

Q16.1b. Did you receive a supply of **tofacitinib patient alert cards** after February 2020?
Please select one.

- Yes
- No
- I don't remember

Data: Single punch.
Ask only if Yes in Q16.1a.

[QUESTION APPLIES TO POLAND ONLY]

Q16.1b. Did you receive a supply of **tofacitinib patient alert cards** after January 2020?
Please select one.

- Yes
- No
- I don't remember

Data: Single punch.
Ask only if Yes in Q16.1a.

[QUESTION APPLIES TO ALL COUNTRIES]

Q16.2. How useful or not useful did you find the **tofacitinib patient alert card** in your
clinical practice?

- Very useful
- Somewhat useful
- Not useful

Data: Single punch.
Ask only if Yes in Q16.1a.

[QUESTION APPLIES TO ALL COUNTRIES]

Q17.1 Are you aware of a **prescriber website for tofacitinib** where you can obtain prescribing information and where you can view and/or download the tofacitinib prescriber brochure, prescriber treatment checklists, and patient alert card? Please select one.

- Yes
- No

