Data: Single punch.

[QUESTION APPLIES TO ALL COUNTRIES]

Q17.2. Have you ever visited the **prescriber website for tofacitinib**? Please select one.

- Yes
- No
- I don't remember

Data: Single punch.
Ask only if Yes in Q17.1

[QUESTION APPLIES TO ALL COUNTRIES]

Q17.3. How useful or not useful do you find the **prescriber website for tofacitinib** in your clinical practice? Please select one.

- Very useful
- Somewhat useful
- Not useful

Data: Single punch.
Ask only if Yes in Q17.2.

Thank you for your participation in this survey

IQVIA Team

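### Section 8.7.6 bases website usefulness on HCPs aware of the website, but both questionnaires ask the usefulness item (Q17.3) only of those who visited it

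*Protocol*

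**What the plan says.** Section 8.7.6 fixes two kinds of base for the usefulness ratings. For each material it is the HCPs who report having received it. For the website it is the HCPs who know of it: "or who were aware of the Xeljanz Prescriber Website, the number and proportion of HCPs finding" the item very, somewhat or not useful. No other category is planned.

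The questionnaires route the website items in three steps, in the same way in Appendix 1 (RA/PsA) and Appendix 2 (UC):

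- Q17.1 asks every respondent, Yes or No, about awareness of a site "where you can obtain prescribing information and where you can view and/or download the tofacitinib prescriber brochure, prescriber treatment checklists, and patient alert card".
- Q17.2 asks whether the respondent has ever visited it (Yes, No, I don't remember), with the instruction "Ask only if Yes in Q17.1".
- Q17.3 asks how useful the site is, with the instruction "Ask only if Yes in Q17.2".

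Section 8.7.1 keeps a survey in the analysis if all its questions are "answered (taking into account skip patterns) by HCPs eligible to participate in the survey". A respondent who is correctly routed past Q17.3 therefore still counts as a complete survey.

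**The concern.** The analysis text and the question filter name different groups. Section 8.7.6 counts everyone with Yes at Q17.1; the instrument collects a rating only from those with Yes at Q17.2. The gap consists of aware HCPs who did not visit or do not remember visiting. They are complete respondents and belong to the stated base, but they cannot have a rating.

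At stake is the meaning of the website percentages in both survey reports. Under the rule as written, not having visited lowers every rating, and a reader of the table could take a low share of useful ratings as poor opinion of the site when it partly reflects few visits. If a programmer instead drops the missing answers, the percentages describe visitors but carry a label that says aware HCPs.

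**Working it through.** The plan states no figure for this item, so there is none to reproduce. The check compares base and filter, then works out the arithmetic consequence.

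**Step 1. Base against filter, by item**

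| Usefulness item | Base in section 8.7.6 | Filter in the questionnaires | Agree? |
|---|---|---|---|
| Brochure, Q13.3 | received | Q13.1a = Yes | yes |
| Checklists, Q14.3, Q15.3 (Germany: Q14.4.i) | received | Q14.1a, Q15.1a (Q14.1.i.a) = Yes | yes |
| Alert card, Q16.2 | received | Q16.1a = Yes | yes |
| Website, Q17.3 | aware (Q17.1 = Yes) | Q17.2 = Yes | **no** |

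For the brochure, for example, the instruction is "Ask only if Yes in Q13.1a", which is the receipt question. Only the website row fails.

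**Step 2. Effect on the percentages**

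Let A be the number of aware HCPs, V the number of those answering Yes to Q17.2, and v = V/A. Let p be the proportion of visitors choosing a given category.

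- Count in the category: p × V.
- Proportion under section 8.7.6: p × V / A = p × v.
- Sum over the three categories: v × (sum of the three p) = v × 1 = v.

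So the categories sum to v, and each is too low by a relative 1 − v. This holds whenever at least one aware HCP does not report a visit. For the weighted results, v is the weighted share.

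**Step 3. Illustration**

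The 300 completed surveys per survey are the target in section 8.5. The documents give no awareness, visit or rating figures, so these are assumptions: 60% aware, so A = 0.60 × 300 = 180; p = 80% for one category; v over a range.

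| v | Asked Q17.3 (180 × v) | In the base, never asked | Reported instead of 80% (0.80 × v) |
|---|---|---|---|
| 25% | 45 | 135 | 20% |
| 50% | 90 | 90 | 40% |
| 75% | 135 | 45 | 60% |
| 90% | 162 | 18 | 72% |

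The awareness rate cancels from the last column; only v matters there. With Q17.2 = Yes as the base, the three categories sum to 100% and the reported figure is 80% in every row.

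**The case against.** The case for leaving this alone has real weight. The item is secondary and descriptive. Section 8.7.1 plans no confidence intervals for attitude outcomes, and the footnotes in section 8.3 leave website awareness out of the effectiveness assessment because the site is a repository. No threshold or sample-size figure depends on it. Section 8.7.2 also commits to reporting how many HCPs used the website, and section 8.7.6 gives counts as well as proportions, so a careful reader could recover the visitor-based percentage and would see that the categories fall short of 100%. Section 8.7.1 lets the SAP modify the analyses outlined in the protocol, so the correction can be made there. All of this stands, and it limits the importance of the point. It does not reconcile the two passages: the protocol itself fixes both the base and the filter, and they disagree.

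A reader might go further and infer the reverse fault in the other tools, since recipients who did not read the brochure or never use a checklist are still asked to rate it. The documents do not support calling that an error. Section 8.7.6 asks for ratings among recipients, and the filters deliver exactly that. A recipient who does not use a checklist can validly call it not useful, and may have stopped using it for that reason. A reader might also object that the tools cannot be compared with one another when the website is rated on another basis. Section 8.7.6 describes each material and the website separately, and the protocol plans no comparison between tools.

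**Conclusion.** The website base in section 8.7.6 is wrong as written, in both surveys. It includes HCPs whom the questionnaire never asks, so each website usefulness percentage is multiplied by the share of aware HCPs who report a visit. That the figures can only be lowered follows from the routing alone. By how much cannot be known from the documents: the fall from 80% to 40% assumes v = 50%, and across the assumed range of 25% to 90% the reported figure runs from 20% to 72%.

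The impact is minor. The finding concerns one secondary item and leaves the awareness, knowledge and adherence results untouched. It does not extend to the brochure, checklists or alert card. The SAP is not at hand and may already use the right base; the protocol text would still need to agree with it.

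**What to change.** In section 8.7.6, define the website base as HCPs answering Yes to Q17.2. Alternatively, keep aware HCPs as the base and add a fourth row for those who had not visited or did not remember and so were not asked; the four rows then sum to 100%. Either version should state the base and its number in the table heading. Leave the recipient-based denominators as they are.

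The change belongs in the analysis text and not in the questionnaire: by the dates in Table 1, the data collection windows of seven of the eight countries had ended by 01 March 2022, before this protocol version of 28 March 2022. It costs one sentence and at most one table row, with no new data, and can be made in the SAP or in the protocol before the final report planned for 18 April 2023.

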8.7.7. Secondary Analysis: Source of HCPs’ Information on the Safety of Xeljanz

The number and proportion of HCPs selecting each pre-populated source of information as their primary source will be reported.

090177e199ebc283\Approved\Approved On: 11-Apr-2022 22:32 (GMT)

8.7.8. Secondary Analysis: Response Rate, Cooperation Rate, Refusal Rate, and Contact Rate

The number of **Targeted HCPs**, and, among them, the number and proportion of Unreachable HCPs, Contacted HCPs, Refused HCPs, Screened Out HCPs, Partial Complete HCPs, and Completed Survey HCPs will be reported. The Contact Rate, Response Rate, Cooperation Rate, and Refusal Rate will also be described.

8.8. Quality Control

QC will be conducted according to Pfizer's Non-Interventional Integrated Quality Control Plan and the standard operating procedures (SOPs) of IQVIA Primary Intelligence and IQVIA Real World Evidence Solutions.

All aspects of the study, from protocol development to the reporting of the results, will be conducted within the framework of the IQVIA Quality Management System.

A QC plan for the study will be developed and executed, which will include QC on the study methodology, SAP, programming, data management and analysis, study results, conclusions, and final study report. Furthermore:

- The study QC plan will establish ownership for the execution of the individual QC steps;
- The Principal in Charge of the study will ensure that individuals responsible for the execution of specific QC steps will have the knowledge, capability, and experience necessary to perform the assigned tasks; and
- The result of the execution of the individual steps of the QC plan will be documented, and will include the required corrective actions, if any. The execution of any required corrective action will also be documented.

The QC plan will be subjected to a final review and approval for sufficiency and completeness from the Principal in Charge of the study. IQVIA will have a qualified individual external to the writing team conduct QC reviews of all final deliverables, which will include the following:

- Confirming that the source of the data and/or results has been documented and that the reported data and/or results have been verified against the source;
- Checking the internal consistency of the results presented in the deliverable;
- Confirming that the conclusions are accurate, objective, balanced, and consistent with other published or released results; and
- Confirming that the format and content of the deliverable are aligned with applicable external requirements.

8.8.1. Approaches for Validating the Questionnaires

The survey questions will be programmed to ensure that they are asked in the appropriate sequence. Skip patterns will be clearly indicated. HCPs will not be able to go back to a question once the question has been answered and they will not be able to skip ahead. Response options presented in a list will be randomised to minimise positional bias. Programming will be reviewed by QC and simulated users (i.e., pilot testing) prior to survey implementation. Surveys will only be allowed to be submitted once all questions have been answered.

Survey items are presented in the following formats:

- Instructions prompting the HCP to indicate whether a series of statements are true or false, or if they do not know the answer (there are also questions that use “yes” or “no” or “I don’t know” as potential response options); and
- Statements or questions asking the HCP to choose from a defined list of possible statements or answers.

The survey was developed jointly by the MAH and IQVIA based on the final approved aRMM materials⁵ and is included in Appendix 1 and Appendix 2 (HCP Questionnaire for the RA/PsA survey and the UC survey, respectively). The survey instrument will be translated from English into the local language for each survey country using a committee-based approach; this method ensures accurate and comprehensive local versions of the survey by a team of translators. Translations will be performed by Research Support Services personnel or qualified vendors, if needed. All translations are performed by certified translators.

8.8.1.1. User Testing of the Survey Instrument

After translations have been completed and prior to fielding the survey, the survey instrument will be pilot-tested by Northwestern University or Research Support Services in each country using a sample of HCPs composed of a minimum of 2-3 specialists (a rheumatologist, dermatologist, and/or gastroenterologist) from each country. Pilot testing will occur in the predominant language of the country. This qualitative testing will assess comprehension among HCPs of the words, phrases, and response options used in the survey to ensure that the intended content of the questions is adequately conveyed. The feedback received from the pilot-testing will be incorporated into the final version of the survey instrument.

8.8.2. Approaches for Validating the Results

The QC for validating the results will be conducted as follows:

1. At the IQVIA Primary Intelligence management level (i.e., survey conduct), every effort will be undertaken to collect, complete, and valid data by:
 - Verification of the reliability and security of the web survey interface by a qualified webmaster for each country; and

- Monitoring the quality and definition of datasets by a qualified data manager.
2. Conducting real-time checks of the answers provided by the HCPs in the background of the web survey.
 3. At the study database level (after merging datasets from each country), final data quality checks will be applied (beyond the data management process) including:
 - Distribution of each variable to count the number of missing values and estimate the associated relative percentage;
 - Estimation of the count and proportion of non-analysable surveys; and
 - Estimation of the count and proportion of non-submitted (i.e., partially completed) surveys.

Any changes in the study database will be tracked and documented. While data from the survey countries will be pooled into a final study database, the country-specific datasets will still be retained in a separate database. Once data are validated and quality checked, the database will be locked.

1. At the statistical analysis level, all data management and statistical analysis programming developed and used in the analysis will be documented. All programming versions generated will be dated, kept with accompanying documentation, and archived. The original study database will be stored according to IQVIA SOPs. A derived database will be created for new versions of the data to allow for recoding and computing of new variables (e.g., combination of modalities for categorical variables).
2. At the results level, a data quality review will be conducted to ensure data integrity. A final study report including all the results will be provided for review and discussion. The final study report will take into account the reviewers' comments.
3. The results validation will be conducted according to the SOPs of IQVIA Real World Evidence Solutions and IQVIA Primary Intelligence divisions.

